## **8 MANAGEMENT OF SPECIFIC ADVERSE EVENTS**

### **8.1 Serious Infections**

Study drug treatments should be withheld if patients experience a serious infection until the infection is believed to have completely resolved. The Investigator should contact the Medical Monitor to discuss whether the patient should return to Study Drug treatment.

### **8.2 Injection-Related Reactions, Hypersensitivity, and Anaphylaxis**

Signs of a possible injection-related reaction include fever, chills, pruritus, and urticaria.

Anaphylaxis is a severe, potentially fatal, systemic allergic reaction that occurs suddenly after contact with an allergy-causing substance, such as an investigational product.

For the purposes of this study, a hypersensitivity reaction is defined as an acute onset of an illness with involvement of the skin, mucosal tissue, or both during injection of the Study Drug (but does not meet the definition of anaphylaxis described above).

If signs and symptoms of injection-related reactions are observed and the patient's cardiovascular status is stable:

- If the patient continues to show signs and symptoms of hypersensitivity, administer an SC dose of antihistamine, if the Investigator believes this is appropriate.
- In patients who have experienced mild or moderate injection reactions during prior Study Drug administrations, antihistamines and/or acetaminophen may be administered prophylactically prior to subsequent injections, at the discretion of the Investigator.
- In patients who experience severe injection-related reactions, anaphylaxis, or hypersensitivity (see definition and grading below):
  - Permanently discontinue the Study Drug
  - Treat the patients as for an anaphylactic reaction with IV antihistamines, corticosteroids, epinephrine, inhaled bronchodilators, and other measures as necessary
  - Obtain a blood sample for the presence of anti-drug antibodies

The patient should remain in the study for continued follow-up, but should receive no further Study Drug.

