### 3.5.4.1 Pharmacokinetic modeling

To date, the Ziltivekimab clinical program is comprised of 2 studies, both of which are placebo-controlled ascending dose studies. In the first of these studies (Study COR-001-01), patients with ESRD were administered intravenous (IV) infusions of study drug every 2 weeks for a total of 6 doses. Ten patients per cohort were randomized in a 1:4 ratio to placebo or Ziltivekimab (2, 6, and 20 mg).

In the second study (Study COR-001-SC1), patients with CKD were administered single subcutaneous (SC) doses of study drug. Four patients per cohort were randomized in a 1:3 ratio to placebo or Ziltivekimab (5, 15, and 50 mg).

The PK parameters are generally consistent with those expected for a monoclonal antibody. Absolute bioavailability (F) of SC administered Ziltivekimab is 69%, and the mean time of occurrence for peak serum Ziltivekimab concentrations ( $t_{max}$ ) after SC dosing ranged from 8 to 15 days, with an absorption half-life of 3 days. Terminal elimination half-lives ( $t_{1/2,z}$ ) differed between the ESRD patients (mean  $t_{1/2,z}$  ranging from 38 to 44 days) and CKD patients (mean  $t_{1/2,z}$  ranging from 48 to 56 days). While these results suggest that the rate of Ziltivekimab elimination may increase with decreasing renal function, a prior observation in rheumatoid arthritis patients that Ziltivekimab clearance is much slower than the glomerular filtration rate implies that the apparent elimination rate difference is not due to renal function *per se*, but more likely other physiological changes that accompany decreased renal function.

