### **9.3 Adverse Events of Special Interest**

The following adverse events of special interest must be reported to the Sponsor within 24 hours of the Investigator's awareness, even if not meeting the definition of a serious adverse event:

- Serious infections.
- Severe injection-related reactions.
- Gastrointestinal perforations.
- Hypersensitivity reaction during study drug administration.
- Anaphylaxis occurring at any time, even if considered unrelated to the study drug. A CRF for the collection of the details of such reactions will be available in the EDC.
- Neutrophil  $<500/\text{mm}^3$  (severe), or neutrophil  $<1000/\text{mm}^3$  (severe) with evidence of concurrent infection. These events will be separately summarized by treatment group and dose.
- Thrombocytopenia (platelet count  $<50,000/\text{mm}^3$  (severe)) or platelet count  $<75,000/\text{mm}^3$  (moderate) with evidence of concurrent TIMI major bleeding. These events will be separately summarized by treatment group and dose.
- Malignancies
- Description of additional safety assessments by treatment group and dose: vital signs, ECG, clinical laboratory, and anti-drug antibodies (binding and neutralizing).

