#### **SAE and Pregnancy Reporting Contact Information**

[REDACTED]  
Telephone: [REDACTED]  
Facsimile: [REDACTED]  
e-mail: [REDACTED]

Hypersensitivity reactions (see [Section 8.2](#)) occurring during the Study Drug injection and anaphylaxis occurring anytime during Weeks 1 – 21 of the study should be reported in the EDC as adverse or serious adverse events on the AE and SAE CRFs within 24 hours of the site’s awareness of the event. Please submit as much information as is available with the initial report.

Corvidia Therapeutics will immediately notify the Investigator about important safety or toxicology information as it becomes available. It is the responsibility of the Investigator to promptly notify the IRB/ IEC about new and relevant safety information regarding the Study Drug, including serious adverse drug reactions involving risk to human subjects, in

accordance with the applicable policies. An unexpected event is one that is not listed by nature or severity in the [Investigator's Brochure](#).

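### The hypersensitivity item counts only reactions during the injection, so delayed non-severe reactions miss the special-interest summary; and Section 8.2 does not settle how a mild urticaria during injection is handled

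*Protocol*

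**What the plan says.** **Timing.** Section 8.2 limits hypersensitivity to an "acute onset of an illness with involvement of the skin, mucosal tissue, or both during injection of the Study Drug", excluding anaphylaxis. Section 9.3, like the safety endpoints in Section 3.1.2, lists "Hypersensitivity reaction during study drug administration" as an event of special interest, with no severity grade. The same list has "Severe injection-related reactions", with no time window, and "Anaphylaxis occurring at any time, even if considered unrelated to the study drug". Section 9.3 requires these events to reach the sponsor within 24 hours. Section 9.7 repeats a 24-hour rule for hypersensitivity reactions "occurring during the Study Drug injection and anaphylaxis occurring anytime during Weeks" 1 to 21. Section 11.4.5.1 summarises the Section 9.3 events by dose group and treatment assignment.

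**Product.** Table 3 gives a single 1 mL subcutaneous injection every 28 days. Section 3.5.4.1 reports that mean time to peak concentration "ranged from 8 to 15 days, with an absorption half-life of 3 days".

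**Management.** Section 8.2 opens: "Signs of a possible injection-related reaction include fever, chills, pruritus, and urticaria". For a patient whose cardiovascular status is stable it then gives three instructions:
- For continuing hypersensitivity signs, a subcutaneous antihistamine at the investigator's judgement.
- After earlier mild or moderate injection reactions, optional premedication before later injections.
- "In patients who experience severe injection-related reactions, anaphylaxis, or hypersensitivity (see definition and grading below"): permanent discontinuation, treatment as for anaphylaxis, and a blood sample for anti-drug antibodies.

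Section 4.3 repeats the third trigger in nearly the same words.

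**The concern.** There are two separate problems, one of counting and one of consistency.

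**Counting.** Allergic reaction to an antibody is a risk this trial sets out to describe by dose. The protocol accepts late onset for anaphylaxis, yet for the milder related event it looks only at the moments of injection. With a drug absorbed over days, that window leaves out most of the time in which a reaction could start. The special-interest row for hypersensitivity would then understate how often such reactions occur, and the sponsor would receive no 24-hour notice of the ones left out.

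**Consistency.** If one mild event fits two instructions with different consequences for further dosing, two sites can each follow the text and reach opposite decisions. That affects exposure, discontinuation counts and the comparability of safety data across an expected 50 to 60 sites.

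**Working it through.** No calculation applies. The check is to classify events by the protocol's own wording.

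**Step 1: which late reactions are of special interest?**

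| Event | Section 8.2 hypersensitivity? | Special interest under 9.3? | Recorded as |
|---|---|---|---|
| Non-severe, non-anaphylactic skin or mucosal reaction starting after the injection | No | No | Ordinary adverse event (serious adverse event if serious) |
| Later severe reaction judged injection-related | No | Yes, no time window stated | Special-interest event |
| Later anaphylaxis | No, excluded by definition | Yes, at any time | Special-interest event |
| Mild urticaria during the injection | Yes | Yes, no grade required | Special-interest event |

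Only the first row escapes. Because Section 11.4.5.1 builds its special-interest summary from the Section 9.3 list, these events are also left out of that summary.

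**Step 2: what else still captures the first row?** Section 9.6 records all adverse events from randomization to Week 32. Section 11.4.5.1 tabulates treatment-emergent events by preferred term, severity and relatedness. The visit lists in Sections 5.3 and 5.4 schedule anti-drug antibody samples at every clinic visit from Day 1 to Week 32. What is lost is the special-interest count, the 24-hour notice and the event-triggered antibody sample of Section 8.2.

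**Step 3: a mild urticaria during injection, under Section 8.2.**
- Urticaria is a named sign of an injection-related reaction. If it is mild, the premedication instruction applies at later injections, so further dosing is implied, though not stated outright.
- Urticaria is also skin involvement. With onset during injection it meets the hypersensitivity definition, which has no severity limit. If the third instruction covers hypersensitivity of any grade, the drug is permanently stopped and the patient is treated as for anaphylaxis.
- The first instruction (an antihistamine if the investigator thinks it appropriate) also concerns hypersensitivity signs and sits beside the third without a boundary.

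**Step 4: does the text say which applies?** It depends on whether severe qualifies only injection-related reactions or the whole list.
- Two features favour the narrower reading. Section 8.2 already defines anaphylaxis as severe, so the word would add nothing there. Sections 3.1.2 and 9.3 place ungraded hypersensitivity beside severe injection-related reactions.
- The text that should decide, the definition and grading said to follow, is not there. The definition stands above the instruction, and Section 8.2 ends with no grading.
- Table 5 in Section 9.5 is a general scale of tolerability and daily activities, and Section 8.2 does not point to it.
- Section 4.3 refers back to Section 8.2, and to Section 4.5, which lists only laboratory triggers.

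The question is therefore open throughout the protocol.

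**The case against.** **The safety net is wider than the definition suggests.** A reader might infer that all later allergic reactions escape the special-interest rules. The documents do not support that: later anaphylaxis and later severe injection-related reactions are listed, serious reactions are reported under Section 9.7, and the rest appear in the adverse event tables. A reader might also infer that antibody data would be missing for late reactors, but scheduled sampling continues. These points stand and confine the gap to delayed, non-severe, non-anaphylactic reactions.

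**Absorbed fraction is not a measure of missed events.** With a half-life of 3 days, 1 − 2^(−t/3 days) gives about 0.016% absorbed after 1 minute (an assumed injection time) and 0.96% after 1 hour. It is tempting to conclude that nearly all hypersensitivity falls outside the window. Nothing in the protocol links the timing of allergic reactions to the fraction absorbed, and the injection time is not stated. The figures show only that the window is short relative to absorption.

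**The conflict may be only an ambiguity.** If severe governs the whole list, mild cases fall under premedication and severe ones under discontinuation, and the conflict disappears. The reference to a grading lends this some support, and Section 4.3 is itself permissive. It is therefore too strong to call the instructions proven contradictions. What stands is that the text does not choose between the readings and the grading is absent.

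**Scope is the sponsor's choice, and widening the definition has a side effect.** What counts as of special interest is a design decision. Widening the Section 8.2 definition itself would also widen the permanent-discontinuation trigger. That is a sound objection, and it is why the reporting scope has to be separated from the management trigger.

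**Conclusion.** The point holds in a limited form.

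1. Sections 3.1.2, 8.2, 9.3 and 9.7 confine hypersensitivity to the injection or administration. Delayed, non-severe, non-anaphylactic reactions are therefore undercounted in the by-dose special-interest summary, while remaining in the general adverse event tables. The size cannot be given as a number, because the documents offer no rate or timing for such reactions.
2. Section 8.2 leaves a mild urticaria during injection under two instructions with different consequences on the plain reading, and under one if severe also qualifies hypersensitivity. Sections 4.3 and 8.2 do not say which, and the promised grading is absent.

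The first conclusion assumes only that an injection is brief. The second rests on the wording as it stands. Neither touches the primary endpoint, the power or the error control, so this is a worthwhile and inexpensive correction and not a condition for the trial to be valid.

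**What to change.** **Reporting and summary (Sections 3.1.2, 9.3 and 9.7 only).** Extend the hypersensitivity item to reactions during or after administration, with a collection window that the sponsor states and justifies. Say explicitly that this scope serves special-interest reporting and the Section 11.4.5.1 summary, and does not alter the management trigger in Sections 4.3 and 8.2.

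**Management (Sections 4.3 and 8.2).** Reconcile the passages: make injection-related reaction and hypersensitivity mutually exclusive categories, state what severe qualifies, and either supply the grading or refer correctly to where it stands. Which management belongs to which category is for the sponsor to decide, and none is proposed here.

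**Cost.** Protocol wording, matching case report form text, and more special-interest reports to process within 24 hours.

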## 9 ADVERSE EVENT REPORTING

### 9.1 Adverse Event Definitions

An AE is any undesirable event or any untoward medical occurrence that occurs to a participant during the course of a study, or the protocol-defined time after study termination, whether or not that event is considered Study Drug-related.

Examples include:

- Any treatment emergent signs and symptoms (events that are marked by a change from the patient's baseline/entry status [e.g., an increase in severity or frequency of pre-existing abnormality or disorder]);
- All reactions from Study Drug, abuse of drug, withdrawal phenomena, sensitivity or toxicity to Study Drug;
- Apparently unrelated illnesses;
- Injuries or accidents (e.g., for a fall secondary to dizziness, record "dizziness" as the event and include the information about the fall in the comment/narrative section and information about any injury secondary to the fall as part of the "outcome");
- Exacerbations (increase in frequency or severity) of symptomatology, subjective patient-reported events, new clinically significant abnormalities in clinical laboratory, physiological testing or physical examination;
- Abnormal laboratory findings considered by the Investigator to be clinically significant. In general, an abnormal laboratory value should not be recorded as an adverse event unless:
  - It is associated with clinical signs or symptoms,
  - Requires an intervention, results in a serious adverse event, or
  - Results in study termination or interruption/discontinuation of study treatment.

However, if none of the above applies, but the laboratory abnormality is considered clinically significantly worsened, it should be reported as a laboratory AE (e.g., "increased white blood cell count"). When recording an adverse event resulting from a laboratory abnormality, the resulting medical condition rather than the abnormality itself should be recorded (e.g., record "anemia" rather than "low hemoglobin").

## 9.2 Serious Adverse Event Definition

An SAE is any AE, occurring at any dose and regardless of causality, that:

- Results in death;
- Is life-threatening. Life-threatening means that in the opinion of the Investigator or Study Sponsor, the patient was at immediate risk of death from the reaction as it occurred, (i.e., it does not include a reaction that hypothetically might have caused death had it occurred in a more severe form);
- Requires inpatient hospitalization or prolongation of existing hospitalization. Hospitalization admissions and/or surgical operations scheduled to occur during the study period, but planned before the signing for the ICF, are not considered AEs if the illness or disease existed before the patient was enrolled in the trial, provided that it did not deteriorate in an unexpected manner during the trial (e.g., surgery performed earlier than planned);
- Results in persistent or significant disability/incapacity. Disability is defined as a substantial disruption of a person's ability to conduct normal life functions;
- Is a congenital anomaly/birth defect;
- Is an important medical event. An important medical event is an event that may not result in death, be life-threatening, or require hospitalization but may be considered an SAE when, based upon appropriate medical judgment, it may jeopardize the patient and may require medical or surgical intervention to prevent one of the outcomes listed in the definitions for SAEs. Examples of such medical events include allergic bronchospasm requiring intensive treatment in an emergency room or at home, blood dyscrasias or convulsions that do not result in inpatient hospitalization, or the development of drug dependency or drug abuse.

A distinction should be made between the terms “serious” and “severe” since they **are not** synonymous. The term “severe” is often used to describe the intensity (severity) of a specific event (as in mild, moderate, or severe myocardial infarction); the event itself, however, may be of relatively minor medical significance (such as severe headache). This is **not** the same as “serious,” which is based on patient/event outcome or action criteria usually associated with events that pose a threat to a patient’s life or functioning. A severe adverse event does not necessarily need to be considered serious. For example, persistent nausea of several hours duration may be considered severe nausea but not an SAE if the event does not meet the serious criteria. On the other hand, a stroke resulting in only a minor degree of disability may be considered mild, but would be defined as an SAE based on the above noted serious

criteria. Seriousness (not severity) serves as a guide for defining regulatory reporting obligations.

### **9.3 Adverse Events of Special Interest**

The following adverse events of special interest must be reported to the Sponsor within 24 hours of the Investigator's awareness, even if not meeting the definition of a serious adverse event:

- Serious infections.
- Severe injection-related reactions.
- Gastrointestinal perforations.
- Hypersensitivity reaction during study drug administration.
- Anaphylaxis occurring at any time, even if considered unrelated to the study drug. A CRF for the collection of the details of such reactions will be available in the EDC.
- Neutrophil  $<500/\text{mm}^3$  (severe), or neutrophil  $<1000/\text{mm}^3$  (severe) with evidence of concurrent infection. These events will be separately summarized by treatment group and dose.
- Thrombocytopenia (platelet count  $<50,000/\text{mm}^3$  (severe)) or platelet count  $<75,000/\text{mm}^3$  (moderate) with evidence of concurrent TIMI major bleeding. These events will be separately summarized by treatment group and dose.
- Malignancies
- Description of additional safety assessments by treatment group and dose: vital signs, ECG, clinical laboratory, and anti-drug antibodies (binding and neutralizing).

### **9.4 Assessment of Causal Relationship**

The causal association of AEs to Study Drug administration should be determined as follows:

The following categories should be used in the causality assessment of suspected adverse reactions:

#### Probable

The AE follows a reasonable temporal sequence from the time of Study Drug administration; and/or follows a known response pattern to the Study Drug; and was unlikely to have been produced by other factors such as the patient's clinical state, therapeutic intervention or concomitant therapy.

#### Possible

The AE follows a reasonable temporal sequence from the time of Study Drug administration; and/or follows a known response pattern to the Study Drug; but could have been produced by

other factors such as the patient's clinical state, therapeutic intervention or concomitant therapy.

Unlikely

The AE does not follow a reasonable temporal sequence from the time of Study Drug administration; and was most likely produced by other factors such as the patient's clinical state, therapeutic intervention or concomitant therapy.

Unrelated

This category is applicable to those AEs that are judged to be clearly and incontrovertibly due only to extraneous causes (the patient's clinical state, therapeutic intervention or concomitant therapy) and do not meet the criteria for Study Drug relationship listed under Probable, Possible, or Unlikely.

An AE with causal relationship not initially determined will require follow-up to assign causality.

## 9.5 Assessment of Severity

The Investigator must determine the severity of the event or laboratory value according to **Table 5** (refer to laboratory manual for guidance); severity describes the intensity of the adverse event or lab value.

**Table 5 Severity Assessment for AEs and Abnormal Laboratory Values**

Mild	Awareness of sign or symptom, but easily tolerated; lab value mildly outside normal reference range but not clinically significant
Moderate	Discomfort enough to cause interference with normal daily activities; lab value moderately outside normal reference range and clinically significant
Severe	Inability to perform normal daily activities; lab value severely outside normal reference range and clinically significant

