### **3.1.2 Safety Endpoints**

- Proportion of patients with AEs, SAEs, severe hematologic AEs, severe non-hematologic AEs, and AEs leading to discontinuation.
- Proportion of subjects with thrombolysis in myocardial infarction (TIMI) major bleeding event.
- Description and frequency of events of special interest by treatment group:
  - Serious infections.
  - Severe injection-related reactions.
  - Gastrointestinal perforations.
  - Hypersensitivity reaction during study drug administration.
  - Anaphylaxis occurring at any time, even if considered unrelated to the study drug. A CRF for the collection of the details of such reactions will be available in the electronic data capture (EDC) system.
  - Neutrophil  $<500/\text{mm}^3$  (severe) or neutrophil  $<1000/\text{mm}^3$  (severe) with evidence of concurrent infection. These events will be separately summarized by treatment group and dose.
  - Thrombocytopenia (platelet count  $<50,000/\text{mm}^3$  [severe]) or platelet count  $<75,000/\text{mm}^3$  (moderate) with evidence of concurrent TIMI major bleeding. These events will be separately summarized by treatment group and dose.
  - Malignancies

- Description of additional safety assessments by treatment group and dose: vital signs, electrocardiogram (ECG), clinical laboratory, and anti-drug antibodies (binding and neutralizing).

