#### **4.5 Temporary Discontinuation of Study Intervention**

Participants may have their study drug administration temporarily suspended during the course of the study. Study drug administration should be temporarily withheld if the participant experiences one or more of the following:

- ALT >3x ULN (moderate)
- Neutrophils <1000/mm^3 (severe)
- Platelet count <50,000/mm^3 (severe)
- Platelet count <75,000/mm^3 (moderate) with evidence of concurrent TIMI major bleeding.

Laboratory measures should be present on two independent assessments. After a temporary suspension of study drug has been performed, study drug may be restarted provided the participant has met the following criteria:

- Neutrophils  $\geq 1500/\text{mm}^3$ , and
- Platelets  $\geq 100,000/\text{mm}^3$

No ongoing clinical sequelae attributable to neutropenia or thrombocytopenia, respectively. If, after restarting study drug, the event causing temporary discontinuation reoccurs study drug should be discontinued permanently.

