## 9.6 Adverse Event Reporting

The AE reporting period starts with randomization and continues through the Week 32 study visit. Patients in this study who experience a drug-related AE or SAE will be followed until the AE or SAE is resolved or stabilizes per the Investigator's judgment, even if this occurs after the final study visit. All AEs spontaneously reported by the patient and/or in response to an open question from study personnel or revealed by observation, physical examination, or other diagnostic procedures will be recorded and reported on the appropriate CRF. When

a unifying diagnosis has been made that accounts for several possible signs and/or symptoms, the unifying diagnosis should be selected as the AE term. For example, the combination of general malaise, mild fever, headache, and rhinitis should be described as “upper respiratory syndrome” if this diagnosis has been made, rather than reporting the individual symptoms as separate events.

If any laboratory test is newly abnormal during the treatment or safety follow-up period, it will be followed at the discretion of the Investigator. Abnormalities of laboratory tests which are, in the opinion of the Investigator, clinically significantly worse compared to baseline, or for which a medical intervention is initiated, should be reported as AEs on the AE CRF.

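### Table 5 grades laboratory values partly on clinical significance, leaves three of six combinations without a grade, and does not match the adverse event rules in 9.1 and 9.6 or the severity labels in 4.5

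*Protocol*

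**What the plan says.** Section 9.5 makes Table 5 the required scale for the severity of both events and laboratory values. It adds a pointer: "refer to laboratory manual for guidance); severity describes the intensity of the adverse event or lab value". For laboratory values the three rows are:

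- mild: "lab value mildly outside normal reference range but not clinically significant"
- moderate: "lab value moderately outside normal reference range and clinically significant"
- severe: "lab value severely outside normal reference range and clinically significant"

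Two sections decide when a laboratory value becomes an AE. Section 9.1 says it generally does not unless it has symptoms, needs an intervention, leads to a serious event, or "Results in study termination or interruption/discontinuation of study treatment". It then adds a further route for values that meet none of these but have worsened to a clinically significant degree. Section 9.6 says that laboratory abnormalities "clinically significantly worse compared to baseline, or for which a medical intervention is initiated, should be reported as AEs".

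Section 4.5, on temporary holds, prints its own labels: "Neutrophils <1000/mm 3 (severe"), platelets below 50,000/mm3 as severe, and ALT above 3 times ULN as moderate. None carries a clinical-significance condition. Laboratory findings must be present on two assessments.

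The safety endpoints in 3.1.2 include the proportions with "severe hematologic AEs, severe non-hematologic AEs, and AEs leading to discontinuation". Section 11.4.5.1 tabulates treatment-emergent AEs by maximum severity and sends the reader to 11.4.5.7 for severe hematologic AEs.

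**The concern.** A severity scale should grade every event that can reach it. Table 5 uses clinical significance as part of the grade, although 9.1 and 9.6 have already used it to decide whether the value is an AE at all. The mild row then excludes the property that brings many laboratory values into the AE data. Section 4.5 meanwhile attaches severity words to specific counts by a different rule, and the protocol does not say how the two relate.

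At stake are the severe hematologic and severe non-hematologic AE proportions and the maximum-severity tables. With approximately 50 to 60 sites, an investigator who meets a case with no matching row must improvise, and different investigators may choose different rows.

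**Working it through.** No sample size, power or error rate bears on this point, so the check sets the text side by side.

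**Step 1. Coverage of Table 5.** Three distances from the normal range times two significance calls gives 3 × 2 = 6 combinations.

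| Distance from range | Clinically significant | Not clinically significant |
|---|---|---|
| Mild | no grade | mild |
| Moderate | moderate | no grade |
| Severe | severe | no grade |

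Graded: 3. Without a grade: 6 − 3 = 3.

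**Step 2. Mild and significant.** A value a little outside range that the investigator considers clinically significantly worse is an AE under 9.1 and 9.6. Section 9.5 then requires a Table 5 grade. The mild row is closed because the value is significant. The moderate and severe rows are closed because the deviation is mild. This gap follows directly from the main route by which laboratory values become AEs.

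**Step 3. Severe and not significant.** Take a symptom-free neutrophil count of 900/mm3 (illustrative), confirmed on a second assessment.

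- Section 4.5: below 1000/mm3, labelled severe, study drug withheld.
- Section 9.1: the value interrupted treatment, so it is recordable as an AE.
- Section 9.5: a Table 5 grade is required.
- Table 5: if the investigator judges the count clinically significant and severely outside range, the grade is severe and agrees with 4.5. If it is judged not significant, no row applies.

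The same path holds for a confirmed, symptom-free platelet count below 50,000/mm3.

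**Step 4. Does another section settle it?** Section 11.4.5.1 refers severe hematologic AEs to 11.4.5.7, but that section holds only the TIMI bleeding classification and gives no neutrophil or platelet severity. The protocol therefore does not say which scheme defines a severe neutrophil or platelet AE.

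**Step 5. What does not depend on Table 5.** The hold rule in 4.5 is triggered by ALT or by counts, with bleeding for one platelet criterion. The neutrophil and platelet events of special interest in 9.3 are triggered by counts, with infection or bleeding where stated. Section 11.4.5.2 summarizes laboratory values and changes from baseline by visit and arm. None of these uses a Table 5 grade.

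**Step 6. Size.** The documents give no frequency for the cases in Steps 2 and 3, so no miscount can be calculated. For scale only: with 60 patients per arm, each patient graded differently moves that arm's proportion by 1/60, about 1.7 percentage points.

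**The case against.** The strongest reply is that the neutrophil example needs an unlikely judgment: a confirmed count low enough to stop dosing, yet called not clinically significant. In 9.1 the interruption route also sits beneath a bullet about clinically significant findings, so it could be argued that a non-significant value never becomes an AE. The first part stands in that the conflict is conditional and may be uncommon. The second does not. Section 9.1 goes on to cover values that meet none of the listed routes but are clinically significantly worsened, which treats interruption as a route separate from the significance call. The gap in Step 2 does not need the unlikely judgment at all.

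A second reply is that the laboratory manual cited in 9.5 is not shown and may hold numeric cut-offs. It may, so the lack of numbers in Table 5 is not itself an error. Cut-offs would define the distance from range; they would not remove the significance clause or fill the three empty combinations.

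Four stronger readings are tempting, and the documents do not support them:

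- *The severe-AE endpoints are miscounted.* Many values judged not significant never become AEs, and no frequency is given. Inconsistent grading is possible but not shown.
- *Dose selection on neutrophils and platelets is compromised.* The count-based events in 9.3 and the laboratory summaries in 11.4.5.2 remain available and do not use Table 5.
- *Sections 4.5 and 9.3 label everything by number alone.* Platelets below 75,000/mm3 are labelled moderate only with concurrent TIMI major bleeding. In 9.3, neutrophils below 1000/mm3 count only with concurrent infection, where a not-significant call is implausible. ALT is not in 9.3.
- *Kidney-disease abnormalities at entry inflate the severe counts.* Table 5 does refer to the normal range while 9.6 refers to baseline. But a laboratory AE under 9.6 must be clinically significantly worse or need intervention, and a treatment-emergent AE must start or worsen after first dose. Stable entry values do not qualify, and any residual effect would be expected in all arms of a randomized, blinded trial.

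**Conclusion.** The point holds as an internal inconsistency in a required grading rule. Table 5 leaves three of six combinations ungraded. It contradicts 9.1 and 9.6 for mildly abnormal but clinically significant laboratory AEs, and it does not match 4.5 for confirmed low neutrophil or platelet counts judged not significant. The severe-AE proportions in 3.1.2 and the maximum-severity tables in 11.4.5.1 can be graded inconsistently as a result. The contribution to the severe hematologic category is itself unclear, because its only cross-reference leads to bleeding.

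The size cannot be computed from the documents. The conclusion rests on reading the interruption route in 9.1 as separate from the significance call. It also assumes that the laboratory manual does not override the wording of Table 5. The hold rule and the count-based events of special interest stand as they are. The correction is worth making because it costs very little.

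**What to change.** 1. Remove the clinical-significance clause from the laboratory part of each row of Table 5. Sections 9.1 and 9.6 already use it to decide whether a value is an AE. All six combinations then have a row.
2. Reconcile Table 5 with the labels printed in 4.5 and 9.3, and state which scheme sets severity for the severe hematologic and severe non-hematologic AE counts.
3. Correct the cross-reference in 11.4.5.1 so that severe hematologic AEs point to a definition that covers what the category is meant to contain. Section 11.4.5.7 covers only TIMI bleeding.
4. Add a table, by arm, of patients who cross the neutrophil and platelet thresholds already printed in the protocol, derived from the laboratory values.

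The cost is a wording change in Table 5 and 11.4.5.1, a matching line in the AE completion guidance, and one derived table from data already collected. No extra tests or patients are needed. No threshold, hold rule or other clinical rule is changed or proposed.
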